#### **7.5.1. Efficacy follow-up**

During the LTFU period, patients who discontinue treatment for reasons other than radiographic disease progression, or withdrawal of consent from the entire study should continue to be assessed by radiographic imaging, PSA and testosterone, ECOG performance status, complete Brief Pain Inventory - Short Form [BPI-SF] and use Opioid therapy according to the protocol schedule, until disease progression or death.

The disease evaluation will be performed according to the methods outlined in Section 7.3.8.

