Subsequent progression / relapse											X (l)

AE: Adverse event; BPI-SF: Brief Pain Inventory - Short Form; CISR-G: Cumulative Illness Score Rating-Geriatrics; CT: Computed tomography scan; D: Day(s); ECOG: Eastern Cooperative Oncology Group; EORTC-QLQ: European Organisation for Research and Treatment of Cancer – Quality of Life Questionnaire; EOT: End of treatment visit; G-CODE: Geriatric Core Dataset; IWRS: Interactive web response system; LTFU: Long-term follow-up visit; MRI: Magnetic resonance imaging; PCWG3: Prostate Cancer Working Group 3 ([Scher, 2016](#)); PSA: Prostate specific antigen; Q: Every; SCN: Screening period (up to 28 days prior to randomisation); V: Visit

- (a) Status of ongoing adverse events and/or new treatment-related adverse events
- (b) If patient discontinued study treatment for a reason other than radiographic disease progression, procedure is to be performed according to the protocol schedule until disease progression.
- (c) Mandatory at the screening visit, to be repeated at subsequent visits only in case of abnormal results or if clinically indicated by patient symptoms
- (d) Haematology: Haemoglobin, Haematocrit, Platelet count, Red blood cell count, White blood cell count (total and differential), Absolute neutrophil count, Lymphocytes
- (e) To be performed within 7 days prior to the first administration of study treatment
- (f) Serum chemistry: Alanine aminotransferase (ALAT), Albumin, Alkaline phosphatase, Aspartate aminotransferase (ASAT), Blood urea nitrogen, Calcium, Chloride, C-reactive protein, Creatinine (With estimated GFR [MDRD or CKI EPI method]), Direct Bilirubin (If total bilirubin is elevated above the upper limit of normal), Gamma-glutamyl transferase (GGT), Glucose, Lactate dehydrogenase, Magnesium, Phosphorus, Potassium, Sodium, Total Bilirubin (+ Direct Bilirubin if total bilirubin is elevated above the upper limit of normal), Total protein, Urea, Uric Acid
- (g) Optional: To be performed only for patients who provide additional informed consent to translational analysis
- (h) Archived Formalin fixed / paraffin embedded (FFPE) biopsy material obtained at time of diagnosis as part of the standard medical care will be collected at study entry.
- (i) At the time of disease progression, if medically feasible.

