### 3.2.2. Secondary endpoint(s)

#### Key secondary endpoints:

- Castration-resistant prostate cancer (CRPC)-free survival, defined as the time from randomisation to onset of CRPC according to PCWG3 criteria, or death, whichever occurs first.
- Clinical progression-free survival, defined as time from randomisation to first occurrence of any one of the following:
  - Cancer pain deterioration (2-point deterioration from baseline according to the Brief Pain Inventory - Short Form [BPI-SF] questionnaire, or initiation of opioid therapy, or a  $\geq 30\%$  increase in opiate use),
  - Any deterioration of physical function measured using the 4-IADL assessment tool,
  - A deterioration in ECOG performance status of at least 2 points from baseline,
  - Death from any cause.
- Overall survival, defined as the time from randomisation to the time of death from any cause. For subjects alive at the time of analysis, data will be censored on the last date the subject was known to be alive or lost to follow-up or withdraw consent.
- Toxicity will be evaluated according to version 5 of the National Cancer Institut - Common Terminology Criteria for Adverse Events (NCI-CTCAE v5.0).

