### Geriatric status

Patient geriatric status will be evaluated using the G8 screening tool, G-CODE assessment tool and CISR-G comorbidity assessment tool.

- The G8 screening tool ([Soubeyran, 2008](#); Appendix 7) was developed to separate fit older cancer patients who were able to receive standard treatment from those that should undergo a geriatric assessment to guide tailoring of therapy. It consists of a short, nurse-administered survey of eight questions to establish: appetite, weight loss, BMI, mobility, mood and cognition, number of medications, patient-related health, age categories.
- The G-CODE ([Paillaud, 2018](#); Appendix 8) is a core set of commonly used tools/items for geriatric assessment which has been validated for the collection of geriatric data in clinical cancer trials of older adults, enabling comparison across trials. The tools/items proposed in G-CODE are:

- (i) Social assessment: living alone or support requested to stay at home;

- (ii) Functional autonomy: Activities of Daily Living (ADL) questionnaire and short instrumental ADL questionnaire (4-IADL);
  - (iii) Mobility: Timed Up and Go test;
  - (iv) Nutrition: weight loss during the past 6 months and body mass index;
  - (v) Cognition: Mini-Cog test;
  - (vi) Mood: mini-Geriatric Depression Scale;
  - (vii) Comorbidity: updated Charlson Comorbidity Index.
- The CISR-G (Miller, 1992; Appendix 9) is a nurse administered questionnaire to record and score the medical and psychiatric impairment of older patients to quantify the overall burden of disease (comorbidity)

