### 7.5. Follow-up

Long-term follow-up assessments will be performed for all patients every 180 ( $\pm$  14) days following the EoT visit.

The following information will be collected at each LTFU assessment:

- Patients survival status.
- Subsequent antineoplastic therapies (including regimen administered [drug, dose, frequency, mode], start and stop dates).
- Efficacy data (including response to subsequent antineoplastic therapies, dates of progression and evaluation of serum PSA levels).
- Status of ongoing AEs and/or new treatment-related AEs.

No study specific evaluations will be performed during the LTFU period, other than those described in Section 7.5.1 below. Data collection will be limited to that information which is available in the patient's medical file and evaluations performed as part of patients continued treatment at the site, or obtained via communication with the patients treating physician or via telephone contact with the patient.

Long-term follow-up will continue until death, withdrawal of consent, or 10 years after date of patient randomisation, whichever occurs first.

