#### **10.3.7. Analysis Specifications**

In general, all hypotheses testing will be performed at a 2-tailed significance level of  $\alpha = 0.05$ . All interval estimations will be reported using 95% confidence intervals.

The following endpoints are considered as key secondary endpoints:

- Castration-resistant prostate cancer-free survival,
- Clinical progression-free survival,
- Overall survival,

Key secondary efficacy endpoints will be tested using the Hochberg test procedure to control the familywise type I error rate; i.e., testing will begin with p value  $P_{(m)}$  with corresponding hypothesis  $H_{(m)}$ , where  $P_{(m)}$  is the largest ordered p values amongst 'm' secondary endpoints (i.e., "the least significant p-value") and  $H_{(m)}$  is the corresponding hypothesis. If  $P_{(m)} \leq \alpha$ , then all null hypotheses are rejected. If not, then  $P_{(j)}$ , the (j)th largest p-value, is compared with  $\alpha/(m-j+1)$ . If smaller, then all

hypotheses from  $H_{(j)}$  to  $H_{(1)}$  are rejected. The testing procedure continues in this manner until no significant result is found. This procedure controls the overall level of significance at the 2-tailed, 0.05 level.

All other endpoints will be considered as exploratory endpoints and will also be analysed. No adjustment for multiple testing will be made. Each endpoint will be tested at a 2-tailed 0.05 level of significance.

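### Clinical PFS counts any 4-IADL decline, but the 4-IADL is not scheduled after the end-of-treatment visit, even where ECOG and BPI-SF follow-up continues

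*Protocol*

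**What the plan says.** Protocol Section 3.2.2 defines cPFS as time from randomisation to the first of four kinds of event:

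- pain: "Cancer pain deterioration (2-point deterioration from baseline according to the Brief Pain Inventory - Short Form [BPI-SF] questionnaire", with opioid start or a rise of at least 30% in opiate use as alternatives;
- function: "Any deterioration of physical function measured using the 4-IADL assessment tool";
- performance status: "A deterioration in ECOG performance status of at least 2 points from baseline";
- death from any cause.

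Radiographic progression is not on the list. Section 10.3.7 names cPFS a key secondary endpoint beside CRPC-free survival and overall survival, and says: "Key secondary efficacy endpoints will be tested using the Hochberg test procedure to control the familywise type I error rate".

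Section 6.3 places the 4-IADL inside the G-CODE. In the schedule of visits the G-CODE is marked at screening, D120, D240, later treatment visits and EoT. Its cell under long-term follow-up (LTFU) is empty.

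Section 7.5 limits what follows EoT: "No study specific evaluations will be performed during the LTFU period, other than those described in Section 7.5.1 below". Section 7.5.1 covers patients who stopped treatment for reasons other than radiographic progression or consent withdrawal. They keep imaging, PSA, testosterone and ECOG, and are to "complete Brief Pain Inventory - Short Form [BPI-SF] and use Opioid therapy according to the protocol schedule, until disease progression or death". In the schedule, the LTFU cells for ECOG, concomitant therapies and BPI-SF carry footnote (b), under which the "procedure is to be performed according to the protocol schedule until disease progression".

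**The concern.** A patient who stops study drug for toxicity or by choice, without a cPFS event, is still at risk for cPFS under the ITT analysis. The protocol recognises this by continuing ECOG, BPI-SF and opioid use, which feed two of the three non-death components. The third, the 4-IADL, is dropped at that point. It has the lowest threshold, since any decline counts.

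From then on a functional decline in such a patient either goes unseen or appears only later, as a pain or ECOG event or as death. The endpoint is then a four-part composite up to EoT and a three-part composite afterwards, with the switch set by when treatment stopped. Section 10.3.2 leaves censoring rules for secondary endpoints to the SAP, but a SAP can only choose how to handle the gap. It cannot supply assessments that were never scheduled.

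A second cut-off applies to patients who stop because of radiographic progression. They are also still at risk for cPFS, but Section 7.5.1 does not apply to them.

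**Working it through.** **1. Each component traced through the schedule**

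| cPFS component | On treatment | EoT visit (7.4) | LTFU, stopped without radiographic progression (7.5.1, footnote b) | LTFU, after radiographic progression (7.5) |
|---|---|---|---|---|
| BPI-SF pain | yes | yes | yes | no |
| Opioid use | yes | yes | yes | no |
| ECOG | yes | yes | yes | no |
| 4-IADL (in G-CODE) | yes | yes | **no** | no |
| Death | yes | yes | yes | yes |

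From D120 onwards the G-CODE and BPI-SF are scheduled at the same treatment visits. The pairing breaks only after EoT. The fourth column is the internal mismatch: three of four inputs continue and one does not.

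**2. How many patients the 4-IADL gap concerns**

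The protocol gives no expected rate of stopping without progression. As an assumption, take the rates of discontinuation for treatment-emergent adverse events that Section 1.4.1 reports from ARAMIS, 8.9% on darolutamide and 8.7% on placebo, with 150 patients per arm:

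- 150 × 0.089 = 13.4 and 150 × 0.087 = 13.1, so about 13 per arm;
- at twice the higher rate, 150 × 0.178 = 26.7, so about 27 per arm.

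ARAMIS enrolled a different population, and these rates exclude patient choice and investigator decision, so the true number may be higher. Patients who already had a cPFS event before stopping lose nothing, which pulls it down.

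**3. The cut-off at radiographic progression**

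The protocol states no figure for cPFS. Its design assumption for rPFS reproduces. With HR 0.65, two-sided 0.05 and 85% power, Schoenfeld gives 4 × (1.960 + 1.036)² / (ln 0.65)² = 194 events and Freedman gives 200, around the stated 197. With the protocol's accrual table and a monthly drop-out hazard of 0.014, about 196.6 events are expected at 75 months.

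Under the design medians of 12 and 18.5 months, the share with an rPFS event by time t is 1 − 0.5^(t/median):

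| t (months) | Control | Experimental |
|---|---|---|
| 12 | 1 − 0.5^(12/12) = 50.0% | 1 − 0.5^(12/18.5) = 36.2% |
| 18.5 | 1 − 0.5^(18.5/12) = 65.7% | 1 − 0.5^(18.5/18.5) = 50.0% |

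These are upper bounds on the patients whose non-death assessment ends for this reason. An rPFS event may be a death, which cPFS captures, and some patients will already have had a cPFS event.

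**4. What the progression cut-off could do (illustration only)**

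Assumptions not in the protocol: death hazard 0.015 per month in both arms; drug acting only by delaying progression; 36 months of follow-up; assessment ending at progression, ignoring the EoT visit. The ratio is the cPFS event rate per person-time, experimental over control.

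| Deterioration hazard before / after progression (per month) | Full follow-up | Censored at progression | Only deaths counted after | Assessment ends before any cPFS event, control vs experimental |
|---|---|---|---|---|
| 0.02 / 0.02 to 0.08 | 1.00 to 0.87 | about 1.00 | about 1.13 | 52% vs 34% |
| 0.04 / 0.08 to 0.12 | 0.93 to 0.89 | about 1.00 | about 1.18 | 42% vs 27% |

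In these settings the distortion runs toward or past the null, against darolutamide.

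**The case against.** A reader might infer that cPFS loses all its non-death components at radiographic progression, that this happens earlier on placebo, and that the test is therefore biased by the margin of 50% against 36%. The documents do not support that.

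- Section 7.4 repeats ECOG, BPI-SF, the G-CODE and concomitant therapies after stopping for any reason, about 30 days after the last dose or before new therapy if sooner. A patient who stops at progression is therefore scheduled for one more full assessment.
- The 50% and 36% are rPFS events, not patients lost to cPFS.
- Earlier loss on placebo follows only if darolutamide delays progression as the design assumes. If it does not, this cut-off falls equally in both arms, and nothing here shows an inflated type I error in the Hochberg family.
- Whether a later deterioration is censored, missed or dated at death depends on SAP rules not shown. The protocol gives no rate of functional or pain decline after progression.

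The limited LTFU also looks deliberate. Section 7.5 relies on file review, the treating physician or telephone, in a frail population. After progression, pain and function also reflect later therapy chosen by the physician. Declining to measure them is a defensible trade-off.

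All of this stands, and it reduces the post-progression issue to a secondary one. It does not answer the 4-IADL omission in patients whom Section 7.5.1 still assesses. Section 5.6 has patients who discontinue continue with protocol-defined procedures, but after EoT those are the procedures of Section 7.5, so it does not restore the 4-IADL.

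**Conclusion.** The 4-IADL omission holds on the text alone and needs no assumption. A key secondary endpoint counts an event that the schedule stops looking for, in patients whose other components are still assessed. Its size is uncertain: about 13 patients per arm at the ARAMIS toxicity rates, about 27 at double, with other reasons for stopping adding and prior cPFS events subtracting. The direction of any effect cannot be fixed from the protocol.

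The cut-off after radiographic progression is real but conditional. If rPFS medians are 12 and 18.5 months, it comes earlier on placebo and could dilute or hide a cPFS benefit. Size and direction rest on hazards the protocol does not give and on the SAP's censoring rules. The likelier harm is lost sensitivity rather than a false claim.

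The primary endpoint, the 197 events, the sample size and the power are unaffected. This should be corrected, but it does not threaten the trial's main conclusion.

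**What to change.** **Main change.** Add the 4-IADL to the list in Section 7.5.1 and to the LTFU column with footnote (b), on the same schedule as ECOG and BPI-SF. The four 4-IADL questions suffice; the full G-CODE is not needed.

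**Reconcile at the same time.** The trial description in the Protocol Summary also ends these assessments at the start of a new antineoplastic treatment. Sections 7 and 7.5.1 do not. The passages should state one stopping point.

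**Option for the sponsor.** After radiographic progression, collect 4-IADL, ECOG, BPI-SF and opioid use at the existing 180-day contact until first cPFS event or death. This is a larger change. It alters the limit set in Section 7.5, ECOG and a self-completed questionnaire are harder to obtain by telephone, and dating is coarser. In patients already past progression, deteriorations would be dated late and two ascertainment regimes would be mixed in one endpoint.

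**Cost of the main change.** A protocol and eCRF amendment, with updated patient information if required, and four more questions at assessments that already take place. Assessments already missed cannot be recovered. With about 115 of 300 patients enrolled at this amendment, most of the trial can still be covered.

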#### **7.6. Provisions in case of treatment or trial interruption**

In cases of patient withdrawal of consent or early trial termination, all efforts should be made to perform the EoT visit assessments (see Section 7.4). The patient's future clinical management will be left to the discretion of the treating physician.

### **8. REPORTING OF ADVERSE EVENTS**

#### **8.1. Adverse events**

##### **8.1.1. General definition of adverse event**

An Adverse Event is defined as any untoward medical occurrence, in a patient or clinical trial subject treated by a medicinal product and which does not necessarily have a causal relationship with this treatment. An AE can therefore be any unfavourable and unintended sign (including an abnormal laboratory finding, for example), symptom, or disease temporally associated with the use of a medicinal product or protocol-specified procedure, whether or not considered related to the medicinal product or protocol-specified procedure. Any worsening (i.e., any clinically significant adverse change in frequency and/or intensity) of a pre-existing condition that is temporally associated with the use of an IMP, is also an AE.

Changes resulting from normal growth and development that do not vary significantly in frequency or severity from expected levels are not to be considered AEs.

Progression of the disease under study is not considered as AE.

An **Adverse Reaction** is a response to an IMP, which is noxious and unintended.

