## **8.2. Serious adverse events**

### **8.2.1. General definition of serious adverse event**

A **Serious Adverse Event (SAE)** is defined as any untoward medical occurrence that at any dose:

- Results in death
- Is life-threatening
- Requires hospitalisation or prolongation of existing hospitalisation
- Results in persistent or significant disability/incapacity
- Is a congenital anomaly/birth defect
- Is medically relevant in the context of the pathology and the clinical trial

These characteristics/consequences are to be considered at the time of the event. For example, regarding a life-threatening event, this refers to an event in which the patient was at risk of death at the time of the event; it does not refer to an event which hypothetically might have caused death if it was more severe.

The terms **disability and incapacity** correspond to any clinically relevant physical or psychological handicap, transient or permanent, which impact the patient's physical condition/activity and/or the quality of life.

Medical and scientific judgment should be exercised in deciding whether other situations should be considered serious, such as important medical events that might not be immediately life-threatening or result in death or hospitalisation, but might jeopardize the patient or might require intervention to prevent one of the other outcomes listed in the definition above (for example: treatment in an emergency room; blood dyscrasias or convulsions that do not result in hospitalisation, etc.).

**Abnormal laboratory results should be reported as SAE** if they possibly put at risk the patient or they require medical intervention to prevent an outcome corresponding to one considered severe according to the criteria.

The following events leading to a hospitalisation or prolongation of hospitalisation **are not considered as SAEs**:

- **Hospitalisation already scheduled before the start of the trial**
- **Hospitalisation required as part of the protocol-specified procedures (e.g. for biopsy, chemotherapy, etc.)**
- **Hospitalisation for social or administrative reason without any associated adverse event**

The following events are considered as SAEs **if they are associated to a seriousness criterion** but should not be managed according to the section [Erreur ! Source du renvoi introuvable.](#) These events do not require immediate reporting and should be reported **only in the eCRF**:

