- **Hospitalisation occurring in the context of tumour relapse or progression of disease under trial,**
- **Relapse or progression of disease under trial,**
- **Events related to relapse or to progression of disease under trial.**
- **Surgery for disease under trial.**

A **Serious Adverse Reaction** is an adverse reaction which results in death, is life-threatening, requires inpatient hospitalisation or prolongation of existing hospitalisation, results in persistent or significant disability or incapacity, or is a congenital anomaly/birth defect.

A **Suspected Unexpected Serious Adverse Reaction (SUSAR)** is defined as any serious adverse reaction, the nature, severity or outcome of which is not consistent with the applicable drug information (e.g. IB for an unapproved investigational product or package insert/SmPC for an approved product).

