### **8.2.3. Reporting instructions for specific events**

#### **8.2.3.1. Overdose**

Use of study treatment in dose in excess of that specified in the protocol is considered to be an overdose.

In the event of overdose, the participant should be observed closely for signs of toxicity. Appropriate supportive treatment should be provided if clinically indicated.

The investigator will use clinical judgment to treat any AE-related to overdose (refer to IB).

In case of study treatment overdose without any associated clinical symptoms or abnormal laboratory results, the event of overdose is to be reported as a SAE using the terminology **“accidental or intentional “darolutamide/placebo” overdose without adverse event”**.

If an AE is associated with an overdose of study treatment, the AE is to be reported as a SAE using the terminology **“EVENT resulting from “darolutamide/placebo” overdose”**, even if no other serious criteria are met ([Section 8.2.1](#)).

All reports of overdose whether associated or not with an AE are to be reported to Unicancer immediately following knowledge of the event.

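### Sections 8.1.1 and 8.2.1 contradict each other on whether disease progression is an adverse event, so sites cannot follow one recording rule

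*Protocol*

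**What the plan says.** - **Section 8.1.1** (AE definition): "Progression of the disease under study is not considered as AE". No exception is made for serious cases.
- **Section 8.1.2** has each AE evaluated for its seriousness, and **section 8.1.3** refers to section 8.2 for AEs that meet a seriousness criterion. An SAE is thus an AE with an added attribute.
- **Section 8.2.1** (SAE definition): an SAE "is defined as any untoward medical occurrence that at any dose" meets one of six listed criteria. The section then says "The following events are considered as SAEs", with the condition "if they are associated to a seriousness criterion". The list covers hospitalisation in the context of "relapse or progression of disease under trial", progression itself, "Events related to relapse or to progression of disease under trial", and surgery for the disease. On routing it says "These events do not require immediate reporting and should be reported" in the eCRF alone.
- **Sections 8.2.3.1 to 8.2.3.4** cover overdose, medication error, misuse and abuse without symptoms or abnormal laboratory results. For overdose, "the event of overdose is to be reported as a SAE using the terminology" is followed by a fixed term stating that no adverse event occurred. The other three are worded alike.
- **Section 10.3.3** tabulates AEs by system organ class, preferred term and worst grade. It gives SAEs and deaths in a listing and allows, if necessary, a rate of treatment-emergent events per 100 subject-years of treatment. It does not mention progression-related events.

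**The concern.** A serious progression is not an AE under one section and is an SAE under another. A site that follows section 8.1.1 enters nothing on the AE pages. A site that follows section 8.2.1 enters an SAE in the eCRF. The safety database then depends on which section a site reads.

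The safety profile is a key secondary objective, and the rationale in section 1.2 rests on acceptable toxicity in frail men. Study treatment runs until radiographic progression, and AEs are collected until 30 days after the last dose. A progression that ends treatment therefore falls inside the collection window. Progression is also the efficacy outcome, so its frequency should differ between arms if the drug works. Safety data that include some progressions would partly reflect efficacy.

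**Working it through.** **1. Can both rules hold?**

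| Event | Section 8.1.1 | Section 8.2.1 |
|---|---|---|
| Progression, no seriousness criterion met | Not an AE | Not an SAE |
| Progression, seriousness criterion met | Not an AE | SAE, eCRF only |

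The first row is consistent and the second is not. Given sections 8.1.2 and 8.1.3, calling the event an SAE makes it an AE, which section 8.1.1 denies. The condition and the eCRF-only route in section 8.2.1 limit how often the conflict arises, but do not remove it.

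**2. Which arm would be affected more?**

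Inputs from section 10.1: median rPFS 12 and 18.5 months; HR 0.65; 150 patients per arm; a dropout hazard of 0.014, read as per month because no unit is given; accrual of 18, 50, 53 and 179 patients over 12, 12, 12 and 24 months; cut-off at month 75.

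Reproduction of the plan's 197 events:
- Schoenfeld's formula, 4 × (1.960 + 1.036)² / (ln 0.65)², gives 194. Freedman's gives 200. With 197 events the power is 85.6%, against the stated 85%.

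Expected events by arm, with exponential times, event hazard λ and dropout hazard δ:
- Leavers = Σ over accrual periods of n × {1 − [exp(−k(75−b)) − exp(−k(75−a))] / [k(b−a)]}, where k = λ + δ, the period runs from month a to month b, and n is half the accrual.
- Events = leavers × λ / k.
- Placebo: λ = ln 2 / 12 = 0.0578 and k = 0.0718. Leavers 133.9; events 133.9 × 0.805 = 107.8.
- Darolutamide: λ = ln 2 / 18.5 = 0.0375 and k = 0.0515. Leavers 122.0; events 122.0 × 0.728 = 88.8.
- Total 196.6, against the stated 197. Dropouts are (26.1 + 33.2) / 300 = 19.8%, close to the stated maximum of 19.3%, which supports the monthly reading of the hazard.

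The plan's model therefore implies about 108 rPFS events on placebo (71.8% of 150) and 89 on darolutamide (59.2%). With no treatment effect both arms share one λ and the expected difference is zero.

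**3. Can this be turned into a number of SAEs?**

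No. That would need the split of rPFS events into progressions and deaths, the share of progressions that are serious, and the share that falls inside the AE window. The protocol gives none of these. Time at risk for rPFS is also not the denominator in section 10.3.3, which uses treatment duration.

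**The case against.** The strongest reply is that nothing in the protocol says these events are counted in a safety comparison, and that their handling belongs in the SAP. Much of this stands, and three stronger readings that a reader might infer are not supported.

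- **That the toxicity endpoint counts efficacy failures.** The endpoint is toxicity graded by CTCAE, and section 8.1.1 keeps progression out of AEs. Section 10.3.3 only lists SAEs, and section 10.3.7 leaves toxicity out of the formally tested key secondary endpoints. Contamination is possible because the text does not settle the matter, but it is not established.
- **That the distortion has a known size.** Any figure would rest on shares that the protocol does not give. It would also have to allow for progressions found after treatment has stopped, since imaging continues and section 10.3.2 counts progression even under later therapy. Those can fall outside the AE window.
- **That dosing errors without symptoms meet no seriousness criterion.** Section 8.2.1 includes medical relevance as a criterion, and section 8.2.3 can be read as choosing a reporting route. The prescribed terms make these reports identifiable, and nothing suggests that they differ by arm in a double-blind trial.

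The appeal to the SAP does not dispose of the recording conflict. An analysis rule can drop or flag what was entered, but it cannot recover what a site following section 8.1.1 never recorded as a safety event.

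**Conclusion.** The protocol is wrong as written on one definite point: sections 8.1.1 and 8.2.1 give incompatible rules for serious progression. This follows from the text and needs no assumption beyond sections 8.1.2 and 8.1.3, which make an SAE a kind of AE.

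The consequence is conditional. If serious progressions enter the AE or SAE data, they would be expected more often on placebo under the design assumptions (HR 0.65, exponential times, the tabulated accrual), which would favour darolutamide. The 108 and 89 events show the direction only. No sample size, power, alpha or efficacy analysis depends on this point.

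The dosing-error wording is secondary. It places reports that state no adverse event under the SAE heading, which sits awkwardly with the definition in section 8.2.1, but they can be separated afterwards.

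**What to change.** 1. Reconcile sections 8.1.1 and 8.2.1 so that one recording rule applies at all sites. Either keep section 8.1.1 and have section 8.2.1 record progression, and hospitalisation in its context, in the eCRF as disease outcomes; or add the serious cases to section 8.1.1 as an explicit exception. Either is workable; having both is not.
2. Add an eCRF flag for progression-related events.
3. State in section 10.3.3 that flagged events are excluded from, or shown separately from, the AE and SAE summaries by arm.
4. Keep the reports under sections 8.2.3.1 to 8.2.3.4 on the same notification route and timeline, and list those without an adverse event separately from SAEs.

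The cost is protocol wording, one eCRF field, and a check of events already entered. The current amendment gives about 115 of 300 patients enrolled, so about 185 can still be recorded under one rule from the start. No immediate reporting is lost.
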